### **Withdrawal Criteria**

1. Discovery of non-compliance with inclusion criteria or fulfillment of exclusion criteria after enrollment;

2. Failure of data de-identification or file corruption;
3. Patients or their legal representatives withdrawing consent during the study period;
4. Occurrence of data security incidents or ethical risks, leading to exclusion as determined by the IRB after review.

#### **(IV) Detailed Research Protocol**

##### **Research Data Sources**

Data for this study are derived from patients undergoing routine clinical examinations in the hospital during the study period. Data collection is accomplished relying on the hospital's existing information systems, without imposing additional burdens on patients or interfering with diagnosis and treatment processes. All data are real-world multimodal information generated in routine clinical practice, mainly including:

- Medical imaging data from the Department of Radiology, covering original images and reconstructed sequences such as CT, MRI, and ultrasound, as well as manual annotations, masks, or structured descriptions, which serve as reference standards for model validation;
- Radiology diagnostic reports, including examination findings, diagnostic conclusions, and physician recommendations. All images undergo unified format conversion (e.g., DICOM to NIfTI) and quality assessment before being imported into the study database, with sequences containing artifacts or defects excluded;
- Text data from the electronic medical record system, including admission records, discharge summaries, progress notes, and surgical records. Prior to import, text data undergo automated de-identification to remove sensitive information such as names, hospital admission numbers, ID card numbers, and contact information, retaining only key clinical course points relevant to the research objectives;
- Structured laboratory data from the laboratory information system, including quantitative data such as complete blood count, biochemical indicators, tumor markers, and coagulation function, which are aligned with imaging examinations via timestamps to support cross-modal feature fusion and quantitative analysis of disease states in the model.

All research data undergo rigorous de-identification before being imported into the analysis environment, with only the minimum necessary information required for the study retained. Data collection and usage comply with the Personal Information Protection Law, Data Security Law, and the hospital's ethical requirements. All patients sign a written informed consent form prior to enrollment, explicitly agreeing to the use of their de-identified data for scientific research model validation and performance optimization. The entire research process is conducted under the approval and supervision of the IRB.

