## **3. Research Design and Methods**

### **Prospective Validation of a Multimodal Imaging Large Model**

#### **(I) Study Design Type and Methodology**

This study is a single-center prospective observational study, aiming to conduct prospective validation and optimization of the established medical multimodal large model based on real-time collected clinical multimodal data (imaging, medical records, laboratory tests, reports, etc.). No additional interventions will be imposed on patients' diagnosis and treatment processes during the study; relevant data will only be collected synchronously during routine clinical examinations and diagnostic procedures, making it a non-interventional, minimal-risk prospective study.

During the study period, all newly diagnosed cases meeting the inclusion criteria will be consecutively enrolled. The research team will conduct prospective inference and performance validation of the multimodal medical large model based on imaging findings, EMR text, and laboratory test data, systematically evaluating the model's performance in tasks such as disease diagnosis, lesion localization, and report generation. Study results will be compared with clinicians' actual diagnostic conclusions and pathological gold standards to verify the model's generalization ability and clinical applicability in real-world scenarios.

The overall study protocol includes the following phases:

1. **Case recruitment and data collection:** Patients undergoing imaging examinations in the hospital will be consecutively recruited according to pre-defined inclusion criteria. Study data are derived from routine clinical workflows, covering imaging data, EMRs, laboratory results, and radiology reports. All data will undergo de-identification and quality control before being entered into the study database, with only the minimum necessary information retained.

2. **Model application and inference:** The research team will deploy the multimodal model in the hospital's secure computing environment. For each enrolled patient, the model will automatically generate disease predictions, lesion localization results, and diagnostic reports based on their imaging data and corresponding clinical text.

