## **(III) Patient Inclusion, Exclusion, and Withdrawal Criteria**

### **Inclusion Criteria**

1. Adult patients aged  $\geq 18$  years;
2. Undergoing imaging examinations (CT, MRI, ultrasound, etc.) in the hospital during the study period;
3. Examination items corresponding to the disease types or systems focused on by the study (hepatobiliary and pancreatic system);
4. Possessing at least complete imaging data and radiology diagnostic reports, with relevant medical record information as supplementary modalities;
5. Patients or their legal representatives signing an informed consent form, agreeing to the use of their de-identified data for scientific research model validation;
6. Case data passing quality review, with good imaging quality and standardized text records.

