#### **Statistical Analysis Procedures**

This study adopts intention-to-treat (ITT) analysis as the primary analytical strategy, conducting systematic statistical analysis on data from all enrolled cases. First, descriptive statistics are performed to summarize the baseline characteristics of patients, including age, gender, disease type, and imaging equipment source. Continuous variables are presented as mean  $\pm$  standard deviation or median depending on their distribution type, while categorical variables are expressed as frequencies. Inter-group differences are analyzed using appropriate statistical methods based on data characteristics: the t-test is used for normally distributed data, and the Mann–Whitney U test is used for non-normally distributed data.

In the analysis of primary outcome indicators, this study focuses on evaluating the model's performance in three core tasks: disease diagnosis, lesion localization, and report generation. For the disease diagnosis task, clinical final diagnosis or pathological results are used as the gold standard to calculate AUC, Sensitivity, Specificity, Accuracy, and F1-score, and receiver operating characteristic (ROC) curves are plotted to comprehensively assess the model's classification ability. For the lesion localization and segmentation task, expert annotations are used as references to calculate the Dice coefficient and Hausdorff distance, measuring the model's performance in lesion recognition range and boundary precision. For the report generation task, model-generated reports are compared with radiologists' reports at the text level, and natural language generation metrics such as BLEU, ROUGE, and CIDEr are used to evaluate language quality and semantic consistency.

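### Record text that can state the final diagnosis may enter model inference, with no time cut-off, so the primary diagnostic accuracy measures can be inflated by leakage

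*Protocol*

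**What the plan says.** **Inputs.** Protocol section 3 (I) plans "prospective inference and performance validation of the multimodal medical large model based on imaging findings, EMR text, and laboratory test data". Its phase on model application says the model will "generate disease predictions, lesion localization results, and diagnostic reports based on their imaging data and corresponding clinical text". The inclusion criteria in section 3 (III) require images and radiology reports, "with relevant medical record information as supplementary modalities".

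**What the record text is.** Section 3 (IV), Research Data Sources, gives the only description: "Text data from the electronic medical record system, including admission records, discharge summaries, progress notes, and surgical records". The text is de-identified and reduced, "retaining only key clinical course points relevant to the research objectives". The same list says that laboratory data are aligned to the imaging by timestamp. It says nothing of the kind for text.

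**Reference standard.** Under Statistical Analysis Procedures, for the diagnosis task, "clinical final diagnosis or pathological results are used as the gold standard". AUC, sensitivity, specificity, accuracy and F1 are all primary outcome indicators. Generated reports are scored against the radiologists' reports.

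**The concern.** A diagnostic accuracy study needs the index test to be blind to the reference standard. Here the index test is a model that reads text, and the text it may read includes documents that usually record the reference result. A discharge summary normally carries the final diagnosis, and a surgical record the operative finding. If such text from the index episode reaches the model, a correct output may reflect reading the diagnosis rather than making it.

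At stake are all five primary measures of the diagnosis task and any claim of the 5-point advantage over manual diagnosis on which the sample size rests. The bias does not shrink with more patients. Once the outputs have been produced from contaminated text, no later analysis of those outputs can repair them.

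**Working it through.** **Step 1: put the sections side by side.**

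| Question | Where in the protocol | Answer |
|---|---|---|
| Is record text a model input? | 3 (I), twice; Inclusion Criteria | Yes |
| Which text? | Research Data Sources | Includes discharge summaries, progress notes, surgical records |
| Is it limited by time? | Nowhere | No; timestamp alignment is stated for laboratory data only, without a cut-off |
| Are diagnosis statements removed? | Research Data Sources | No; the filter removes identifiers and keeps relevant clinical course points, which would tend to keep a diagnosis |
| What is the model scored against? | Statistical Analysis Procedures | Final clinical diagnosis or pathology |

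Inputs and reference can overlap, and no section separates them.

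**Step 2: how large could it be?** The protocol gives no leak share, so there is no plan figure to reproduce. The one anchor is in the sample size text: 85% model accuracy against 80% manual accuracy, a difference of 5 points. (The group sizes derived there are a separate matter and do not enter here.)

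Assumptions, not from the documents: accuracy without leakage p = 0.80; where the text states the diagnosis, the model returns it correctly with probability c = 0.98; L is the share of cases in which it does.

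Apparent accuracy = L × c + (1 − L) × p = 0.80 + 0.18 × L

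- L = 0.10: 0.80 + 0.018 = 81.8%
- L = 0.20: 0.80 + 0.036 = 83.6%
- L = 0.30: 0.80 + 0.054 = 85.4%

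Leak share that alone gives 5 points: 0.05 / 0.18 = 0.278, about 28%. With perfect copying (c = 1) it is 0.05 / 0.20 = 25%.

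**Step 3: what would that do to the comparison?** Suppose model and manual accuracy are both truly 80%, copying is perfect, and the groups are independent with 1000 each (half of the planned 2000, because the plan words its calculation per group). The test is two-sided at 0.05. At L = 0.20 the apparent accuracy is 84%:

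- Standard error under no difference: √(2 × 0.82 × 0.18 / 1000) = 0.01718
- Standard error under 84% against 80%: √((0.84 × 0.16 + 0.80 × 0.20) / 1000) = 0.01716
- Chance of a significant result in the model's favour: Φ((0.04 − 1.96 × 0.01718) / 0.01716) = Φ(0.37), about 64%

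The same calculation gives about 8% at L = 0.05, 21% at 0.10, 84% at 0.25 and 95% at 0.30.

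**The case against.** The strongest reply is that Research Data Sources lists what the study collects, not what the model reads. The list plainly mixes roles: its first item includes annotations and masks that serve as reference standards. Discharge summaries and surgical records may be there to establish the final diagnosis, especially as no pathology system is listed. Real-time collection and prospective inference are also compatible with running the model near the time of imaging, when an index-episode discharge summary would not yet exist. Patients need not be admitted to be eligible, so many may have no such document. A summary from an earlier episode is legitimate history.

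Much of this stands. It means that leakage is possible rather than certain, and that the leak share could be close to zero. It does not remove the defect. Section 3 (I) makes record text an input, the list is the only account of what that text is, it gives these documents no reference-only role, and no time of inference is fixed.

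A reader might go further in three ways that the documents do not support:

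- **That accuracy is inflated.** No sentence says that these particular documents enter inference. The link comes from reading two sections together.
- **That BLEU, ROUGE and CIDEr will measure copying.** This holds only if the term imaging findings in section 3 (I) means the radiologist's report text. It may mean just the images, as the parallel wording in the per-patient step suggests.
- **That the comparison with clinicians is unfair because they diagnosed before these records existed.** The protocol does not say when the clinicians' conclusions were reached.

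**Conclusion.** The point holds in this form: the protocol permits the reference diagnosis to reach the model through record text, and contains no rule that prevents it. The primary diagnosis measures can therefore be inflated, by an amount that cannot be computed from the documents. The figures of 81.8% to 85.4%, and the 28% leak share that would by itself create the planned advantage, rest on the assumed 80% accuracy without leakage, 98% copying and chosen leak shares. They show that moderate leakage would be enough to matter; they do not predict what this study will find. Report generation is at similar risk only under one reading of an ambiguous term.

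This is not a detail to leave to a statistical analysis plan. The protocol itself sets both the inputs and the reference standard, and the inputs are fixed once inference is run. It should be settled before the first case is processed.

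**What to change.** In section 3 (I) and in Research Data Sources, state that:

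1. Only text and laboratory results time-stamped before the index imaging report is signed may enter inference.
2. The index radiology report, findings and conclusion alike, is not an input. This also settles the ambiguity for report generation.
3. Later records (index-episode discharge summary, surgical record, pathology, later progress notes) serve only to establish the reference standard.

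Records from earlier episodes that meet the cut-off may stay, so a blanket bar on discharge summaries or surgical records is not needed.

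The cost is one filter in the data pipeline. It assumes that record entries carry usable timestamps, as the protocol says laboratory data do. Because the filter acts on timestamps, it can be applied whenever inference is run. The downside is less text input and probably a lower measured accuracy, but one that can be read as diagnostic performance.

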### **Exclusion Criteria**

1. Patients refusing to sign the informed consent form;
2. Imaging data unassessable due to severe motion artifacts, incomplete scanning, or equipment malfunctions;
3. Severe lack of clinical data or inability to match with imaging data;
4. Special pathological cases or post-operative cases (e.g., extensive resection, significant structural changes after radiotherapy) that affect the consistency of model analysis;
5. Data samples with privacy protection or legal risks.

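### The protocol sets no time limit on the record text given to the model, so documents stating the final diagnosis may enter the input and inflate the primary diagnosis metrics

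*Protocol*

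**What the plan says.** Section 3 (I) of the protocol, Study Design Type and Methodology, describes "prospective inference and performance validation of the multimodal medical large model based on imaging findings, EMR text, and laboratory test data". The inference phase in the same section says that "the model will automatically generate disease predictions, lesion localization results, and diagnostic reports based on their imaging data and corresponding clinical text". Inclusion criterion 4 requires imaging and radiology reports, "with relevant medical record information as supplementary modalities".

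Section 3 (IV), Research Data Sources, is the only place that says what the record text consists of: "Text data from the electronic medical record system, including admission records, discharge summaries, progress notes, and surgical records". Before import, identifiers are removed, "retaining only key clinical course points relevant to the research objectives". Alignment with the imaging examination by timestamp is stated for laboratory data and not for text.

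Under Statistical Analysis Procedures, "clinical final diagnosis or pathological results are used as the gold standard to calculate AUC, Sensitivity, Specificity, Accuracy, and F1-score". These five measures are the primary outcomes of the diagnosis task.

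**The concern.** A discharge summary is written at the end of a stay and normally carries the discharge diagnosis. A record of an operation done after the scan carries the operative finding. Later progress notes may carry either. These are the facts that make up the reference standard. If they are in the input, a model with a language backbone (section 4, Retrospective Study Phase) can take the diagnosis from the text without recognising the disease on the image.

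The measured performance would then not be the performance available when the scan is read. Such use would also conflict with section 3 (I), which presents the data as collected in real time and the inference as prospective, because a discharge summary does not exist at that moment. Enrolling more patients does not reduce a bias of this kind.

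**Working it through.** **Text check**

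| Question | Where | Answer |
|---|---|---|
| Is record text a model input? | Section 3 (I), design statement and inference phase; inclusion criterion 4 | Yes |
| What does record text include? | Section 3 (IV), Research Data Sources | Admission records, discharge summaries, progress notes, surgical records |
| Is there a time cut-off on the text? | All sections | None stated |
| Is diagnostic content removed? | Research Data Sources | No. Identifiers are removed and key course points are kept |
| What is the reference standard? | Statistical Analysis Procedures | Final clinical diagnosis or pathology |
| Is input text kept apart from reference text? | All sections | Not stated |

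The filter on course points does not close the gap. It keeps what is relevant to the research objectives, and disease diagnosis is one of them. The timestamp alignment of laboratory data does not say whether values after the scan are excluded.

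**Illustration of size**

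The plan gives no figure for leakage, so there is none to reproduce. Two figures come from the Sample Size Estimation Process: 85% assumed model accuracy and 80% assumed manual accuracy. Let p0 be accuracy without leakage, p1 accuracy in leaked cases, and L the share of leaked cases. Both p1 and L are assumptions, and so is setting p0 at 80% or 75%.

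Apparent accuracy = (1 − L) × p0 + L × p1, so L = (0.85 − p0) / (p1 − p0) gives an apparent 85%.

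| p0 | p1 = 0.95 | p1 = 0.97 | p1 = 0.99 | p1 = 1.00 |
|---|---|---|---|---|
| 0.80 | 0.05/0.15 = 33% | 0.05/0.17 = 29% | 0.05/0.19 = 26% | 0.05/0.20 = 25% |
| 0.75 | 0.10/0.20 = 50% | 0.10/0.22 = 45% | 0.10/0.24 = 42% | 0.10/0.25 = 40% |

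Smaller shares matter less. With p0 = 0.80 and p1 = 1.00, L = 5%, 10% and 20% give 0.80 + 0.20 × L = 81%, 82% and 84%.

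The same mixture applies to sensitivity among patients with the disease and to specificity among those without it. AUC and F1 move in the same direction, but putting numbers on them would need score distributions and disease frequencies that the protocol does not give.

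**The case against.** **The data list is not an input list.** Research Data Sources says what is collected. It mixes inputs with reference material such as annotations and masks, and it names no separate source for the final diagnosis. Discharge summaries and surgical records may be collected at least partly to supply it. The inference phase refers only to corresponding clinical text, without naming note types. This stands in part: the protocol does not say that discharge summaries are fed to the model. But it uses the same term for the input and for the collected text, and places no restriction between them. Feeding in all four note types would comply with the plan.

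**A cut-off may be set elsewhere.** It may. But what the model receives is a matter of design and data import, which this protocol addresses in two places, and there the input overlaps with the reference standard.

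**Stronger readings that the documents do not support:**

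- A reader might infer that the surgical records must post-date the scan because "Special pathological cases or post-operative cases" are excluded. That exclusion is limited to cases affecting the consistency of model analysis, with extensive resection as an example. Patients with lesser earlier surgery can remain, so some surgical records may pre-date the scan.
- A reader might infer that the comparison with manual diagnosis favours the model because the clinicians lacked these notes. No section says so. Section 3 (I) refers to the clinicians' actual conclusions, and they may have had the full record.
- A reader might go on to compute the chance of a false claim of superiority with 2000 patients. That needs an assumed leakage share and an assumed paired test. The sample size text speaks of cases per group, and no test is named for this comparison.
- A reader might infer that the retained course points are chosen with knowledge of the diagnosis. Nothing says how they are chosen.

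**The share of affected patients may be small.** Eligibility covers anyone having relevant imaging, and outpatients may have no discharge summary or surgical record. This stands, and it is why the figures above are illustrations only.

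**Conclusion.** Wrong as written. The plan makes record text an input, describes that text so as to include documents that normally state the final diagnosis, sets no time limit on it, and scores the model against that same diagnosis. It therefore permits leakage into every primary diagnosis metric, and such leakage would be at odds with its own description of prospective inference. It does not show that leakage will occur.

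The size is unknown. If true accuracy is 80% and leaked cases are 95% to 100% correct, leakage in about 33% to 25% of cases would account for the whole assumed 5-point advantage. The documents give neither the share nor the accuracy in such cases. The conclusion also rests on the ordinary understanding of when a discharge summary is written and what it contains. Bias in the comparison with manual diagnosis remains open until the protocol says what the clinicians could see.

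**What to change.** In section 3 (I) and in Research Data Sources, limit inference inputs to entries time-stamped up to the reading of the index scan. Apply the same rule to text and to laboratory values. Reserve discharge summaries, surgical records of later operations and later progress notes for establishing the reference diagnosis, and state that they do not enter the model input. Also state what information the clinicians had when they made the manual diagnosis, so that the comparison can be interpreted.

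The cost is a wording change and a timestamp filter at data import, with no extra patients and no change to the sample size. The downside is less input text per patient and probably a lower reported accuracy.
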